## 6.1. Critical Baseline Assessments

A signed written informed consent form must be obtained prior to Screening assessments, and before any study-specific assessments for Baseline assessments are initiated.

Baseline level is the basal value required for comparing examination/observation data after the infusion of investigational drug. Therefore, the examination at pre-dose is normally performed. If the data are not examined at Day 0, values at screening will be used as baseline levels.

### 6.1.1. Screening Test

During the screening visit, each subject will have the following evaluations to determine eligibility for enrollment:

- Demographic information including gender, ethnic origin, race, date of birth.
- Medical history, including cardiovascular history and risk factors.
- Complete physical examination, including height.
- Vital signs including temperature, sitting blood pressure, and heart rate.
- Confirm classification of SLE disease (based on ACR criteria) by reviewing previously documented clinical records.
- Clinical laboratory tests:
  - Hematology: White blood cells (WBC), Red blood cells (RBC), Hemoglobin (Hb), Hematocrit (Ht), platelet count and WBC-differential

- Chemistry: AST, ALT, Alkaline phosphatase ( ALP), Gamma glutamyltransferase (GGT), Lactate dehydrogenase (LDH), creatinine, Blood urea nitrogen (BUN), total bilirubin, total protein, albumin, uric acid, Prothrombin time (PT), Partial Thromboplastin Time (PTT), Erythrocyte Sedimentation Rate (ESR), CRP, glucose, sodium, potassium, magnesium, chloride, carbon dioxide (CO2), calcium, phosphate
- Urinalysis: protein, glucose, ketones, occult blood, microscopic examination
- Spot urine for proteinuria assessment
- Urine drug/alcohol screen.
- HIV antibody, Hepatitis B surface antigen, anti-HBc, HBV DNA and Hepatitis C antibody.( NOTE: if anti-HBc result is reactive, the sample drawn for HBV DNA will be tested for viral DNA; otherwise, the sample will be destroyed).
- Serum Pregnancy test.
- Chest X ray.
- 12-lead ECG.
- Immunoglobulins (IgG, IgM and IgA) and auto antibodies (anti-dsDNA, ANA).
- Adverse events.

### **6.1.2. Pre-dose Examination**

Pre-dose examination will be conducted before the dose:

- Adverse events.
- Body weight.
- Vital signs including temperature, sitting blood pressure, and heart rate.
- Current medical history.
- Clinical laboratory tests: hematology, chemistry and urinalysis.
- Urinary pregnancy test (for female only).
- 12-lead ECG.
- Inclusion/exclusion criteria check
- PK blood sampling.

- B cell subsets (CD20+, CD20+/27+ memory, CD20+/27-naïve, CD20+/69+ activated, CD20+/138+ plasmacytoid, CD19+/27BRIGHT/38BRIGHT SLE subset and CD20-/138+ plasma cells)

## 6.2. Safety

The following will be made as the safety assessments.

- Adverse events.
- Clinical laboratory tests: hematology, chemistry and urinalysis.
- Vital signs (blood pressure, heart rate and body temperature).
- 12-lead ECG.

### 6.2.1. Liver Chemistry Follow-up Procedures

**Liver chemistry withdrawal criteria** have been designed to assure subject safety and evaluate liver event etiology.

Liver chemistry stopping criteria 1-3 are defined below:

- 1 ALT  $\geq 3xULN$  **and** bilirubin  $\geq 2xULN$  (>35% direct bilirubin) (or ALT  $\geq 3xULN$  **and** international normalised ratio (INR) >1.5, if INR measure).

NOTE: if serum bilirubin fractionation is not immediately available, study drug should be discontinued if ALT  $\geq 3xULN$  and bilirubin  $\geq 2xULN$ . Serum bilirubin fractionation should be performed if testing is available. If testing is unavailable, **record presence of detectable urinary bilirubin on dipstick**, indicating direct bilirubin elevations and suggesting liver injury.

- 2 ALT  $\geq 5xULN$ .
- 3 ALT  $\geq 3xULN$  if associated with the appearance or worsening of symptoms of hepatitis or hypersensitivity such as fatigue, nausea, vomiting, right upper quadrant pain or tenderness, fever, rash or eosinophilia.

**When any of the liver chemistry withdrawal criteria is met, do the following:**

- Report the event to GSK **within 24 hours** of learning its occurrence
- Complete the liver event CRF and SAE data collection tool if the event also meets the criteria for an SAE. All events of ALT  $\geq 3xULN$  **and** bilirubin  $\geq 2xULN$  (>35% direct bilirubin) (or ALT  $\geq 3xULN$  **and** INR >1.5, if INR measured; INR measurement is not required and the threshold value stated will not apply to patients receiving anticoagulants), termed 'Hy's Law', **must be reported as an SAE (excluding studies of hepatic impairment or cirrhosis)**.

NOTE: if serum bilirubin fractionation is not immediately available, study drug should be discontinued if ALT  $\geq 3 \times \text{ULN}$  **and** bilirubin  $\geq 2 \times \text{ULN}$ . Serum bilirubin fractionation should be performed if testing is available. If testing is unavailable, **record presence of detectable urinary bilirubin on dipstick**, indicating direct bilirubin elevations and suggesting liver injury.

- Complete the liver imaging and/or liver biopsy CRFs if these tests are performed
- Perform liver event follow up assessments, and monitor the subject until liver chemistries resolve, stabilize, or return to baseline values as described below.
- Withdraw the subject from the **study** (unless further safety follow up is required) after completion of the liver chemistry monitoring as described below.

In addition, for criterion 1:

- Make every reasonable attempt to have subjects return to clinic within **24 hours** for repeat liver chemistries, liver event follow up assessments (see below), and close monitoring
- A specialist or hepatology consultation is recommended
- Monitor subjects twice weekly until liver chemistries (ALT, AST, alkaline phosphatase, bilirubin) resolve, stabilize or return to within baseline values

For criteria 2 and 3:

- Make every reasonable attempt to have subjects return to clinic **within 24-72 hrs** for repeat liver chemistries and liver event follow up assessments (see below)
- Monitor subjects weekly until liver chemistries (ALT, AST, alkaline phosphatase, bilirubin) resolve, stabilize or return to within baseline values; criterion 5 subjects should be monitored as frequently as possible.
- Subjects with ALT  $\geq 3 \times \text{ULN}$  **but**  $< 5 \times \text{ULN}$  **and** bilirubin  $< 2 \times \text{ULN}$ , without hepatitis symptoms or rash, and who can be monitored weekly for 4 weeks
- Notify the GSK medical monitor within 24 hours of learning of the abnormality to discuss subject safety.
- Must return weekly for repeat liver chemistries (ALT, AST, alkaline phosphatase, bilirubin) until they resolve, stabilize or return to within baseline
- If at any time these subjects meet the liver chemistry stopping criteria, proceed as described above
- If, after 4 weeks of monitoring, ALT  $< 3 \times \text{ULN}$  and bilirubin  $< 2 \times \text{ULN}$ , monitor subjects twice monthly until liver chemistries normalize or return to within baseline values.

For criteria 1-3, make every attempt to carry out the **liver event follow up assessments** described below:

- Viral hepatitis serology including:
  - Hepatitis A IgM antibody;
  - Hepatitis B surface antigen and Hepatitis B Core Antibody (IgM);
  - Hepatitis C ribonucleic acid (RNA);
  - Cytomegalovirus IgM antibody;
  - Epstein-Barr viral capsid antigen IgM antibody (or if unavailable, obtain heterophile antibody or monospot testing);
  - Hepatitis E IgM antibody
- Blood sample for pharmacokinetic (PK) analysis, obtained within one to two weeks after the liver event. Record the date/time of the PK blood sample draw and the date/time of the last dose of IP prior to blood sample draw on the CRF. If the date or time of the last dose is unclear, provide the subject's best approximation. If the date/time of the last dose cannot be approximated OR a PK sample cannot be collected in the time period indicated above, do not obtain a PK sample. Instructions for sample handling and shipping are in the SPM.
- Serum creatine phosphokinase (CPK) and lactate dehydrogenase (LDH).
- Fractionate bilirubin, if total bilirubin  $\geq 2xULN$
- Obtain complete blood count with differential to assess eosinophilia
- Record the appearance or worsening of clinical symptoms of hepatitis, or hypersensitivity, such as fatigue, nausea, vomiting, right upper quadrant pain or tenderness, fever rash or eosinophilia as relevant on the AE report form
- Record use of concomitant medications, acetaminophen, herbal remedies, other over the counter medications, or putative hepatotoxins, on the concomitant medications report form.
- Record alcohol use on the liver event alcohol intake case report form

The following are required for subjects with ALT  $\geq 3xULN$  and bilirubin  $\geq 2xULN$  ( $>35\%$  direct) but are optional for other abnormal liver chemistries:

- Anti-nuclear antibody, anti-smooth muscle antibody, and Type 1 anti-liver kidney microsomal antibodies, total IgG.

- Liver imaging (ultrasound, magnetic resonance, or computerized tomography) to evaluate liver disease.

#### **6.2.1.1. Additional Hepatitis B Monitoring**

Safety assessment for Hepatitis B during the trial will be as follows:

- ALT and/or AST elevations of greater than 2.5 x ULN will require:
  - Sites to review screening laboratory results for anti-HBc:
    - If screening anti-HBc result was reactive, then obtain HBV DNA.
      - If HBV DNA returns reactive, investigator will determine the extent of required attention for proper follow up of potential hepatitis B re-activation.
    - If screening anti-HBc result was negative, then repeating hepatitis B testing is optional per investigator upon investigating for other causes.

Refer to the SPM for guidance on documenting the suspected reason for ALT and/or AST elevations of greater than 2.5 x ULN.

#### **6.2.2. Clinical Laboratory**

Blood and urine will be taken for clinical laboratory test at screening and at pre-dose, and Days 0, 1, 14, 28, 56 and 84 post-dose.

- Hematology: WBC, RBC, Hb, Ht, PT, PTT, platelet count and WBC-differential (including ESR on screening)
- Chemistry: AST, ALT, ALP, GGT, LDH, creatinine, BUN, total bilirubin, total protein, albumin, uric acid, glucose, sodium, potassium, magnesium, chloride, carbon dioxide, calcium, phosphate (including CRP on screening)
- Urinalysis: protein, glucose, ketones, occult blood, microscopic examination
- Spot urine for proteinuria assessment

Note: ALT and/or AST elevations of greater than 2.5 x ULN will require Hepatitis B assessment, see Section [6.2.1.1](#)

All clinical laboratory blood samples will be sent to a central laboratory for analysis (details provided in the SPM). The central laboratory will fax laboratory results to the Investigator and will transmit the results electronically to GlaxoSmithKline.

#### **6.2.3. Vital Signs**

Systolic and diastolic blood pressure (sitting), heart rate, and body temperature will be measured. Measurements of vital signs will be taken at screening and at pre-dose, and at 5 minutes, 1, 6 and 24 hours, and Days 1, 7, 14, 21, 28, 42, 56 and 84 post-dose.

At the discretion of the Investigator, vital signs may be assessed at unscheduled visits.

#### **6.2.4. 12-Lead ECG**

Measurements of 12-Lead ECG will be taken at screening and at pre-dose, and 24 hours and Day 84 post-dose. The ECG parameters are HR, PR, QRS, QT and QTc.

#### **6.3. Pharmacokinetics**

Blood samples will be collected for PK at pre-dose, and at 5 minutes, 1, 6 and 24 hours, and Days 1, 7, 14, 21, 28, 42, 56 and 84 post-dose. The actual date and time of sampling will be recorded in the CRF. Serum will be harvested within one hour of blood sample collection. PK samples will be sent to a local bioanalytical laboratory and analyzed using a validated method (details provided in the SPM).

#### **6.4. Pharmacodynamic/Biomarkers**

Blood samples will be collected at screening and at pre-dose, Days 14, 28, 42, 56 and 84 post-dose. The actual date and time of sampling will be recorded in the CRF. All blood samples will be sent to a central laboratory for analysis (details provided in the SPM). The central laboratory will fax the results to the Investigator and will transmit the results electronically to GlaxoSmithKline.

- B cell subsets (CD20+, CD20+/27+ memory, CD20+/27- naïve, CD20+/69+activated, CD20+/138+ plasmacytoid, CD19+/27BRIGHT/38BRIGHT SLE subset and CD20-/138+ plasma cells).

### **7. ADVERSE EVENTS, SERIOUS ADVERSE EVENTS, PREGNANCY AND MEDICAL DEVICE INCIDENTS**

#### **7.1. Adverse Events (AE) and Serious Adverse Events (SAEs)**

The investigator or site staff is responsible for detecting, documenting and reporting events that meet the definition of an AE or SAE.

##### **7.1.1. Time period for collecting AEs and SAE information**

AEs will be collected from the start of Study Treatment and until the Day 84 or study discontinuation. Medical occurrences that begin prior to the start of study treatment but after obtaining informed consent may be recorded on the Medical History/Current Medical Conditions CRF.

Serious AEs will be recorded from the time the consent form is signed until the follow-up contact. All SAEs will be recorded and reported to GSK within 24 hours.

Investigators are not obligated to actively seek AEs or SAEs in former study participants. However, if the investigator learns of any SAE, including a death, at any time after a subject has been discharged from the study, and he/she considers the event reasonably related to the study treatment or study participation, the investigator would promptly notify GSK.

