Experience from open-label, long-term continuation trials of belimumab in SLE patients confirms prolonged treatment with belimumab is generally well tolerated. There is no apparent increase in the incidence rate of adverse events (AEs) or serious adverse events (SAEs) over time, including important events such as infections and malignancies. Long term belimumab treatment appears to provide sustained improvement in SLE disease activity and reduction of flares. The definitive assessment of the PK of belimumab is based on a population approach including data collected from subjects with SLE in the Phase 1 (LBSL01), Phase 2 (LBSL02), and Phase 3 (C1056 and C1057) studies. The PK of belimumab administered by IV infusion was well described by a linear 2-compartment model with clearance from the central compartment. After IV infusion, serum belimumab concentrations declined in a bi-exponential manner, with a distribution half-life of 1.1-1.8 days. The terminal half-life is 12.5 days for the 1 mg/kg dose and 19.4 days for the 10 mg/kg dose.

Further information is provided in the Investigator Brochure (IB) ([Belimumab Investigator's Brochure](#)).

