#### 3.3. Discussion of Study Design

##### 3.3.1. Design Rationale

This study is designed to assess the pharmacokinetics, safety, tolerability, and pharmacodynamics of a single intravenous 10mg/kg GSK1550188 dose in Chinese subjects with SLE. The study is open-label as the primary endpoint (pharmacokinetic parameters) will not be influenced by subjects knowing that they are receiving active treatment. The

subjects will have pharmacokinetic samples collected for 84 days (more than five half-lives) after dosing to enable a comprehensive pharmacokinetic profile to be generated. The pharmacokinetics of a single intravenous 10mg/kg GSK1550188 dose has never been assessed in healthy subjects, but has been assessed in Japanese (Study BEL114243) and Western subjects (Study LBSL01) with SLE. Therefore, Chinese subjects with SLE instead of Chinese healthy subjects will be recruited for this study to allow unbiased comparison between Chinese and non-Chinese subjects, if necessary.

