### **4.3. Withdrawal Criteria and Procedures**

A subject may withdraw from study treatment at any time at his/her own request, or may be withdrawn at any time at the discretion of the investigator for safety, behavioral or administrative reasons.

Should a subject fail to attend the clinic for a required study visit, the site should attempt to contact the subject and re-schedule the missed visit as soon as possible. The site should also counsel the subject on the importance of maintaining the assigned visit schedule and ascertain whether or not the subject wishes to and/or should continue in the study based on previous non-compliance. In cases where the subject does not return for the rescheduled visit or cannot be reached to reschedule the missed visit, the site should make every effort to regain contact with the subject (3 telephone calls and if necessary a certified letter to the subject's last known mailing address) so that they can appropriately be withdrawn from the study.

These contact attempts should be documented in the subject's medical record. Should the subject continue to be unreachable, then and only then will he/she be considered to have withdrawn from the study with a primary reason of "Lost to Follow-up". For all other subjects withdrawing from the study, an alternative reason for discontinuation should be recorded in the Case Report Form (CRF). If a subject prematurely withdraws from participation in the study for any reason, the investigator/sub-investigator must make every effort to assess the items specified on discontinuation test.

Refer to Section 5.2.1 for Liver Chemistry stopping criteria, Section 5.2.2 for QTc withdrawal and Section 7.2 for Pregnancy.

Liver chemistry threshold stopping criteria have been designed to assure subject safety and to evaluate liver event etiology (in alignment with the Food and Drug Administration [FDA] premarketing clinical liver safety guidance). See Section 5.2.1 for details.

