#### **7.1.11. Follow-Up of AEs and SAEs**

After the initial AE/SAE report, the investigator (or sub-investigator) is required to proactively follow each subject and provide further information to GSK on the subject’s condition. All AEs and SAEs documented at a previous visit/contact and that are designated as ongoing, will be reviewed at subsequent visits/contacts.

All AEs and SAEs will be followed until resolution, until the condition stabilizes, until the event is otherwise explained, or until the subject is lost to follow-up. This applies to all subjects, including those withdrawn prematurely. The investigator (or sub-investigator) will ensure that follow-up includes any supplemental investigations as may be indicated to elucidate the nature and/or causality of the AE or SAE. This may include additional laboratory tests or investigations, histopathological examinations, or consultation with other health care professionals.

GSK may request that the investigator perform or arrange for the conduct of supplemental measurements and/or evaluations to elucidate as fully as possible the nature and/or causality of the AE or SAE. The investigator (or sub-investigator) is obligated to assist. If a subject dies during participation in the study or during a recognized follow-up period, the investigator will provide GSK with a copy of any post-mortem findings, including histopathology (may not be required for studies where death is an endpoint).

New or updated information will be recorded in the originally completed SAE data collection tool. The investigator (or sub-investigator) will submit the updated SAE data to GSK within the designated reporting time frames.

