9. SECONDARY STATISTICAL ANALYSES

9.1. Safety Analyses

9.1.1. Overview of Adverse Events

The CRF texts for adverse events (AEs) will be coded using MedDRA version 19.0 or above, and will be reported using the System Organ Class (SOC) and Preferred Term (PT). In the summary of AEs, the incidence of AEs will be the number of subjects reporting AEs and not the number of AEs reported. Multiple occurrences of the same AE in one individual will be counted only once when calculating the number and percentage of subjects.

The following AEs will be summarized and listed:

- All AEs;
- All AEs by maximum intensity
- All drug-related AEs
- All drug-related AEs by maximum intensity
- All Serious AEs
- All AEs leading to study withdrawals

More details can be found in Section [9.1.2](#).

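### AE collection ends when a subject leaves the study although the single dose is still on board, so new events after withdrawal are not sought and crude AE percentages may be modestly understated

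*Protocol*

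**What the plan says.** - **End of AE collection.** Protocol 7.1.1: "AEs will be collected from the start of Study Treatment and until the Day 84 or study discontinuation". It adds: "Investigators are not obligated to actively seek AEs or SAEs in former study participants". Section 7.1.12 repeats this. A later SAE is notified only if the investigator hears of it and considers it related to treatment or participation. No route is given for a later non-serious AE.
- **End of SAE recording.** Protocol 7.1.1: "Serious AEs will be recorded from the time the consent form is signed until the follow-up contact". Table 2 has no contact of that name.
- **At withdrawal.** Protocol 4.3 asks that "the investigator/sub-investigator must make every effort to assess the items specified on discontinuation test", and the discontinuation column of Table 2 includes an AE/SAE review. Section 7.1.11 follows events already reported until they resolve or stabilise: "This applies to all subjects, including those withdrawn prematurely".
- **Withdrawal by the protocol.** Section 5.2.2 takes a subject who meets a QTc criterion out of the study. Scheduled post-dose ECGs are at 24 hours and Day 84 (6.2.4). Under section 6.2.1 and Appendix 1, subjects who meet liver criteria leave only after liver monitoring is complete.
- **Exposure.** Protocol 1.1.2: "The terminal half-life is 12.5 days for the 1 mg/kg dose and 19.4 days for the 10 mg/kg dose".
- **Reporting.** SAP section 5 puts every dosed subject in the Safety population. SAP 9.1.1 says "the incidence of AEs will be the number of subjects reporting AEs and not the number of AEs reported". SAP 11.5.1 keeps the data collected before withdrawal and does not replace withdrawn subjects. SAP Tables 2.01–2.06 (11.8.5) list no follow-up time and no exposure-adjusted rate.

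**The concern.** After a single infusion there is no further treatment to stop. A subject who leaves on Day 14 has received the same dose as one who stays to Day 84; only observation is cut short. Tying AE collection to study discontinuation therefore leaves a still-exposed subject unobserved.

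Two consequences follow. First, a delayed reaction may never be recorded. Protocol 3.4 describes delayed non-acute hypersensitivity with onset 4 to 21 days after dosing. A QTc withdrawal at the 24-hour ECG would end the search for new events before that window opens, so a subject removed for a safety signal could be among the least observed. Second, the percentages in the AE tables are proportions of all dosed subjects, with unequal and unreported follow-up. In a study whose secondary objective is safety and tolerability, they would tend to read low.

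**Working it through.** **The plan's own figure.** Protocol 3.3.1 says "subjects will have pharmacokinetic samples collected for 84 days (more than five half-lives) after dosing". With the 10 mg/kg half-life, 84 / 19.4 = 4.33 half-lives, and five half-lives take 5 × 19.4 = 97 days. Only the 1 mg/kg value gives more than five (84 / 12.5 = 6.72). So exposure at the study dose spans the whole planned follow-up. The precision figures in Protocol 9.2.1 concern PK only and are not affected by this point.

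**Exposure left at withdrawal.** Fraction of the terminal-phase level = 0.5^(day / 19.4), a single exponential that ignores the short distribution phase.

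- Day 14: 0.5^(14/19.4) = 0.606, about 61%
- Day 28: 0.5^(28/19.4) = 0.368, about 37%
- Day 84: 0.5^(84/19.4) = 0.050, about 5%

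**Observation lost with a QTc withdrawal at 24 hours.** 84 − 1 = 83 days.

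**Effect on the crude percentage.** The documents give no dropout rate, no withdrawal times and no AE rate, so every input here except N and the 84 days is an assumption. Take N = 20 dosed, k leaving on day d, an 84-day risk p at constant hazard, and withdrawal unrelated to the event. Then:

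expected reported incidence = [(20 − k)p + k(1 − (1 − p)^(d/84))] / 20

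For p = 30%, d = 14, k = 2:

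- risk observed by Day 14 in a subject who leaves: 1 − 0.7^(14/84) = 5.8%
- reported: (18 × 0.30 + 2 × 0.058) / 20 = 27.6%, short by 2.4 points
- subject-days not observed: 2 × 70 / (20 × 84) = 140 / 1680 = 8.3%

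Reported incidence for p = 30% over a range of assumptions:

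| Leave on | 2 of 20 | 4 of 20 |
|---|---|---|
| Day 7 | 27.3% | 24.6% |
| Day 14 | 27.6% | 25.2% |
| Day 28 | 28.1% | 26.2% |
| Day 56 | 29.1% | 28.2% |

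With 2 leaving between Day 7 and Day 56 and p from 10% to 50%, the shortfall runs from 0.3 to 4.4 points.

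**If events cluster early.** Put the same 30% risk entirely in the first 21 days at constant hazard. A subject leaving at Day 14 has then passed 1 − 0.7^(14/21) = 21.2% of risk, and 2 leavers give (18 × 0.30 + 2 × 0.212) / 20 = 29.1%. The shortfall drops from 2.4 to 0.9 points. This does not help a subject who leaves at 24 hours, for whom a window of 4 to 21 days is missed entirely.

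**The case against.** **Withdrawn subjects are not simply event-free.** A reader might infer that early leavers enter the tables as non-cases. The documents do not support that. Events up to the discontinuation visit are collected and kept, a subject withdrawn because of an AE is a case and appears in SAP Table 2.06, and ongoing events are followed after withdrawal. Leavers count as event-free only for terms not reported before they left. This stands.

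**A large bias cannot be claimed.** Enrolling about 20 to keep 12 (Protocol 4.1) may suggest that 8 dosed subjects could drop out. With 8 leaving at Day 14, the formula gives (12 × 0.30 + 8 × 0.058) / 20 = 20.3%. But the 12 are subjects who complete dosing and critical assessments. The other 8 may include subjects never dosed, who are outside the Safety population, or subjects without usable PK who remain under AE follow-up. Neither 8 dropouts nor a 30% risk has support in the text. This stands too.

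**Existing safeguards.** Missed visits are rescheduled, and three calls and if necessary a certified letter precede a lost-to-follow-up classification (Protocol 4.3). Disposition is tabulated (SAP Table 1.01), and withdrawals and AEs are listed by subject (SAP Listings 2 and 13), so in a study this small a careful reader could see who left. Telephone calls cannot recover subjects who are unreachable or refuse contact.

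**Early clustering.** Protocol 3.4 places most serious hypersensitivity during the infusion or within an hour of its end, so the constant-hazard figures probably overstate the loss for that class of event.

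**The SAE wording.** The follow-up contact can naturally be read as the last scheduled visit. It is a wording gap, not evidence of bias.

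None of these points supplies a route for a new non-serious AE after withdrawal, or an active search for a new SAE, in a subject who remains exposed and would accept a call.

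**Conclusion.** The point holds in a limited form. Protocol 7.1.1 stops the search for new events when a subject leaves the study, although leaving does not shorten exposure, and the SAP gives that subject the same weight as one followed for 84 days. Crude AE percentages may therefore be modestly understated, and a delayed event in a withdrawn subject may go unrecorded.

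The size cannot be fixed from the documents. The illustration of about 28% reported against 30% true rests on 2 of 20 leaving at Day 14, constant hazard, and withdrawal unrelated to the event. Fewer or later withdrawals make it smaller, as does clustering of events before a subject leaves; more or earlier withdrawals make it larger. The study is single-arm and descriptive, so no test, comparison or PK estimate changes. It is worth correcting because safety is a stated objective and the remedy is cheap.

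**What to change.** 1. **Protocol 7.1.1.** Replace the end of collection with wording such as: *AEs and SAEs are collected to Day 84 for every dosed subject, including those withdrawn from study visits, by telephone on the scheduled visit days, unless the subject declines contact or cannot be reached.* Make 7.1.12 agree. This concerns data collection only and leaves the withdrawal criteria as they are.
2. **SAE window.** Tie the follow-up contact in 7.1.1 to a contact that exists in Table 2.
3. **SAP Tables 2.01–2.06.** Report alongside them the number of subjects followed to Day 84 and the total follow-up time. Dosing and withdrawal dates suffice for this, even where contact is refused.

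**Cost.** Protocol and SAP wording, and a few calls for the few subjects who withdraw. Telephone reporting after the last visit is already used for pregnancy, up to 16 weeks after the dose (Protocol 7.2 and Table 2, footnote 6). The limit is that data from subjects who are lost to follow-up or refuse contact are not recovered.
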